### **Secondary Outcomes:**

1. Explore effect of core MDD symptoms, cognitive function, and functionality from baseline through eight weeks of treatment with vortioxetine:
  - a. Depressive symptoms
    - i. HDRS-17 total score
    - ii. QIDS-SR-16 total score
    - iii. HDRS-28 total score
    - iv. Response defined as  $\geq 50\%$  decrease in MADRS total score
    - v. Remission defined as  $< 11$  MADRS total score at endpoint
    - vi. Asymptomatic remission defined as MADRS total score  $< 4$
    - vii. Cognition and functionality
    - viii. MGH-CPFQ total score
    - ix. PDQ
    - x. TMT-A/B
    - xi. Stroop Test
    - xii. UPSA
    - xiii. WLQ
  - b. Global clinical status
    - i. CGI-Severity
    - ii. CGI-Improvement
2. Explore effect of core MDD symptoms, cognitive function, and functionality from baseline to endpoint following treatment with vortioxetine and the relationship between changes in BNA patterns from baseline to endpoint on:
  - a. Depressive symptoms (change from baseline to endpoint)
    - i. HDRS-17 total score
    - ii. QIDS-SR-16 total score
    - iii. HDRS-28 total score
    - iv. Response defined as  $\geq 50\%$  decrease in MADRS total score
    - v. Remission defined as  $< 11$  MADRS total score at endpoint
    - vi. Asymptomatic remission defined as MADRS total score  $< 4$
  - b. Cognition and functionality (change from baseline to endpoint)
    - i. MGH-CPFQ total score
    - ii. PDQ
    - iii. TMT-A/B
    - iv. Stroop Test
    - v. UPSA
    - vi. WLQ
  - c. Global clinical status (change from baseline to endpoint)
    - i. CGI-Severity

- ii. CGI-Improvement
- 3. To explore changes in BNA patterns from baseline in predicting clinical outcome at endpoint on:
  - a. Depressive symptoms (change from baseline, 2 week, 8 week)
    - i. MADRS total score
    - ii. HDRS-17 total score
    - iii. HDRS-28 total score
    - iv. QIDS-SR-16 total score
  - b. Cognitive function and functionality (change form baseline, 2 week , 8 week)
    - i. MGH-CPFQ total
    - ii. PDQ
    - iii. WLQ
  - c. Clinical global status (change from baseline, 2 week, 8 week)
    - i. CGI-Severity
    - ii. CGI-Improvement
- 4. To explore differences in BNA patterns and identify potential neural pathways that may impact core depressive symptoms different from cognitive function:
  - a. Explore differences in patterns of BNA changes from baseline to endpoint between:
    - i. Subjects meeting antidepressant efficacy criteria (based on response and remission criteria for MADRS, HRSD, QIDS) and improvement in cognition (based DSST).
    - ii. Subjects failing to meet antidepressant efficacy criteria (based on response criteria for MADRS, HRSD, QIDS) but show improvement in cognition (based on DSST).
    - iii. Subjects failing to meet antidepressant efficacy criteria (based on response criteria for MADRS, HRSD, QIDS) and failing to show improvement in cognition (based on DSST).
    - iv.
    - v.
- 5. To explore changes in BNA patterns in MDD with cognitive dysfunction prior to receiving treatment with vortioxetine and:
  - a. Severity of MDD as measured by baseline MADRS total score, QIDS-SR-16 total score, HDRS-28 item total score and CGI-Severity.
  - b. Severity of cognition dysfunction and functionality as measured by baseline DSST, TMT-A/B, TMT-B, Stroop, MGH-CPFQ total score, UPSA, WLQ.
  - c. Prediction of achieving symptomatic remission of MDD as measured by remission status on MADRS total score, HDRS-17 total score and CGI-Improvement (1 or 2)
  - d. Prediction of cognitive improvement measured by DSST score; cutoff 70% improvement from baseline.
- 6. Explore relationship with changes in BNA patterns in remitted vs. non-remitted subjects after 8 weeks of treatment with vortioxetine as measured by MADRS total score, HDRS-17 total score, QIDS total score,, and CGI-Improvement.
- 7. Assess safety and tolerability of 8 weeks open-label, flexible-dose vortioxetine in all subjects for:
  - a. Spontaneously reported adverse events
  - b. Clinical safety laboratory tests (when indicated, vital signs, weight, EKGs and physical exam)

- c. Evaluate relationship between adverse events after 2 and 8 weeks of treatment with changes in BNA patterns for nausea, worsening of baseline suicidal ideation (as measured by MADRS item 10, HDRS-17 item 2 and C-SSRS)

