## **OUTCOMES**

### **Primary Outcome:**

The primary outcome of this study is to explore changes in BNA patterns from baseline to endpoint with 1) antidepressant response status; response defined as  $\geq 50\%$  change in total MADRS score from baseline to endpoint and, 2) change in cognitive function defined as change from baseline to endpoint on change in total number of correct symbols on the DSST .

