### **Outcome Definitions**

- Remission (Primary Remission Criteria)
  - MADRS total score  $\leq$  10; CGI-I  $<$  2
- Remission (Secondary Remission Criteria)
  - Score  $\leq$  7 of first 17 items of the HDRS (28-item)
  - QIDS-SR16 total score  $<$  5
- Asymptomatic Remission
  - MADRS total score  $\leq$  4
- Response (Primary Response Criteria)
  - $\geq$ 50% decrease in MADRS total score from baseline
- Response (Secondary Response Criteria)
  - $\geq$ 50% decrease from baseline of first 17 items of the HDRS (28-item)
  - $\geq$ 50% decrease from baseline in total score of HDRS (28-item)
  - $\geq$ 50% decrease from baseline in total score of QIDS-SR 16
  - $\geq$ 50% decrease from baseline in total score of MGH-CPFQ
- Non-Remitted (Primary)
  - MADRS total score  $>$  10
- Non-response
  - Change in MADRS total score from baseline  $<$  25%, and MADRS total score  $>$  10
- Inadequate response
  - Change in MADRS total score from baseline 25-49%, and MADRS total score  $>$  10

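### Secondary outcome 4a defines antidepressant success by response and remission but failure by response alone, so DSST improvers who respond without remitting fall in none of its three printed groups

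*Combined protocol and SAP*

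**What the plan says.** Under Secondary Outcomes, item 4a lists the groups whose BNA change from baseline to endpoint is to be compared:

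- Group i reads: "Subjects meeting antidepressant efficacy criteria (based on response and remission criteria for MADRS, HRSD, QIDS) and improvement in cognition", with cognition judged on the DSST.
- Group ii reads: "Subjects failing to meet antidepressant efficacy criteria (based on response criteria for MADRS, HRSD, QIDS) but show improvement in cognition (based on DSST").
- Group iii reads: "Subjects failing to meet antidepressant efficacy criteria (based on response criteria for MADRS, HRSD, QIDS) and failing to show improvement in cognition (based on DSST").

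Sub-items iv and v are printed without text in the supplied document.

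Outcome Definitions gives response and remission different thresholds. Under "Response (Primary Response Criteria") it requires a decrease of at least 50% in MADRS total from baseline. Under "Remission (Primary Remission Criteria") it requires a MADRS total of 10 or less, with a CGI-I condition. The Primary Outcome also works from "antidepressant response status; response defined as" a change of at least 50% in MADRS total. The Rationale for the Proposed Study describes three subgroups: cognition and mood both improved, cognition improved without antidepressant efficacy, and neither improved. It mentions no intermediate mood category.

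**The concern.** The same phrase about efficacy criteria carries two meanings within one comparison. Meeting the criteria takes response and remission; failing them takes only non-response. These are not complements, and the subjects between them have no place.

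Groups i and ii both consist of DSST improvers and differ in mood outcome, so their contrast bears most directly on the item's aim of separating mood-related from cognition-related pathways. With the middle removed it becomes an extreme-groups comparison. If BNA change tracks mood change, the observed separation would be larger than under a simple efficacy/no-efficacy split. Statistical Analyses says the pilot's data will help design a confirmatory study, so an inflated separation could carry forward. If the gap stays open, someone must also decide where these subjects belong once BNA results are available.

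**Working it through.** The plan states no figure for this item, so there is none to reproduce. The check is logical first, then numerical.

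**Inputs from the document.** Entry MADRS of at least 26 (Main Criteria for Inclusion). Response: decrease of at least 50% in MADRS total. Remission: MADRS total of 10 or less (Outcome Definitions); Secondary Outcomes uses below 11, the same integer cut; Secondary Efficacy Analyses uses below 10. Sample size 40.

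**Step 1: remission implies response.** At the lowest eligible baseline, reaching 10 is a decrease of (26 - 10)/26 = 61.5%. Higher baselines need larger decreases. On the MADRS, group i's double requirement therefore reduces to remission, while ii and iii use non-response.

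**Step 2: assignment as written.**

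| Mood outcome | DSST improved | DSST not improved |
|---|---|---|
| Response and remission | i | none |
| Response, no remission | **none** | none |
| No response | ii | iii |

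The bold cell is the point made here. Responders without DSST improvement are also unlisted, but that is a separate matter.

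**Step 3: endpoint scores in the gap.** The gap is 10 < endpoint ≤ baseline/2.

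| Baseline MADRS | Baseline/2 | Unassigned endpoint scores |
|---|---|---|
| 26 | 13 | 11-13 |
| 30 | 15 | 11-15 |
| 34 | 17 | 11-17 |
| 40 | 20 | 11-20 |

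No baseline from 26 to 60 has an empty gap. With the below-10 cut, each range starts at 10. The added CGI-I condition can only make remission harder to reach.

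**Step 4: size, on assumptions that are not in the documents.** Assume a baseline MADRS mean of 31-33 (SD 4-5, truncated at 26), a mean decrease of 45-65% with SD 27%, and percentage change independent of baseline. Simulating endpoint = baseline × (1 - proportional decrease) gives:

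- Response without remission: 22-27% of subjects (40 × 0.22 = 8.8 to 40 × 0.27 = 10.8), which is 34-55% of all responders.
- Baseline of remitters relative to non-responders: about 0.4-0.9 MADRS points lower.

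Only DSST improvers leave the i-versus-ii contrast. Suppose 10-30% of subjects respond without remitting and, independently, 30-70% of those improve on the DSST. The number lost is then 40 × 0.10 × 0.30 = 1.2 to 40 × 0.30 × 0.70 = 8.4, or about 1 to 8 subjects. Using the simulated 22-27% instead gives 40 × 0.22 × 0.30 = 2.6 to 40 × 0.27 × 0.70 = 7.6, inside that range.

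**Step 5: one rule on both sides.** If response and its complement define mood in every group, each DSST improver with endpoint data falls in i or ii, and the bold cell disappears.

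**The case against.** The strongest reply is that the wording may name the sets of criteria to be applied and not require both at once. Outcome Definitions lists response and remission separately for each scale, and Statistical Analyses mentions them as separate example groupings. Read as either/or, group i reduces to response on the MADRS and the gap closes. That reading is possible, but the text says *and*, and groups ii and iii omit remission. The suggested edit would make the either/or reading explicit.

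The blank sub-items iv and v may once have held further groups. That cannot be settled from the supplied text. The rationale lists only three subgroups, and extra groups would not reconcile the two definitions used in i and ii.

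The consequence is also limited. The outcome is secondary and exploratory in a pilot with no sample size calculation. The affected subjects remain in the primary response analysis, in item 2 and in item 6. Comparing remitters with non-responders is a legitimate exploratory contrast if labelled as such. All of this stands and bears on the weight of the point, not on its existence.

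Three stronger readings are tempting and are not supported:

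- **That naming MADRS, HRSD and QIDS opens a second gap, or necessarily widens this one.** The plan does not say whether the scales combine by all or by any. If all three must be met, a MADRS responder who is not a QIDS responder simply fails the set. Whether three scales enlarge or shrink the gap depends on inputs that the documents do not give.
- **That 9-11 of 40 subjects are lost.** That figure counts every responder without remission, including those with no DSST gain.
- **That group i is markedly skewed to milder illness.** Under the same assumptions its baseline is less than one MADRS point below that of non-responders, on a 60-point scale.

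**Conclusion.** The inconsistency is real on the printed text. Group i and groups ii/iii use different mood rules, and DSST improvers who respond without remitting belong to none of groups i-iii. This follows from the plan's own thresholds and entry criterion. It holds under either remission cut, provided that response and remission are read as jointly required.

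The size is uncertain because every rate is assumed: perhaps 1 to 8 of 40 subjects lost from the contrast. With 40 subjects spread over at least three cells, even a few matter for the pattern comparison. It is worth correcting before analysis, but it does not touch the primary outcome or any powered test.

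**What to change.** Use one mood rule in all item 4 groups:

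- Mood improved: the primary response criterion, a decrease of at least 50% in MADRS total.
- Mood not improved: its complement, stated to cover both the inadequate-response and the non-response categories in Outcome Definitions.

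Delete remission from group i. Repeat the grouping separately by HRSD response and by QIDS response, not as joint conditions. Leave remitted versus non-remitted to item 6, which already covers it.

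The cost is a wording edit with no new data or visits. The downside is that group i becomes noticeably less extreme, since 34-55% of responders under the assumptions above are not remitters. If the sharper contrast is wanted, keep remitters versus non-responders as a labelled sensitivity analysis. Item 4 also gives no cutoff for DSST improvement (item 5d uses 70%), so one must be stated before the groups can be formed.

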### Number of Subjects:

40 subjects enrolled. For purposes of IRB reporting, an enrolled subject is one who signs informed consent. For purposes of data analysis and reporting to the funding organization, an enrolled subject is one who meets all inclusion criteria and no exclusion criteria and completes the baseline visit including the baseline BNA.

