**Main Criteria for Exclusion:**

- The subject has a score of  $\geq 70$  on the DSST at the Baseline Visit.
- Failure to respond to or inability to tolerate an adequate trial of vortioxetine in the past.
- Exposure to an investigational compound 30 days prior to enrollment
- Exposure to any psychoactive or otherwise excluded medication within five half-lives of the baseline visit or during the study. Excluded medications include: antidepressants, anxiolytics, anticonvulsants, barbiturates, chloral hydrate, lithium, antipsychotics, benzodiazepines, hypnotics, MAO-Inhibitors, muscle relaxers, triptans, centrally-acting antihistamines, central alpha-2 agonists, decongestants, psychostimulants, dopamine agonists, opioid pain medications, oral corticosteroids, L-methylfolate, SAMe, 5-HTP, St. John's Wort.
- The subject has 1 or more of the following:
  - Primary psychiatric disorder other than MDD as defined in the DSM-IV-TR (as assessed by the MINI, Version 6.0.0).

- Current or history of attention deficit hyperactivity disorder (ADHD), pervasive developmental disorder, manic or hypomanic episode, schizophrenia, or any other psychotic disorder, including major depression with psychotic features, mental retardation, organic mental disorders, or mental disorders due to a general medical condition as defined in the DSM-IV-TR.
- Current diagnosis of alcohol or other substance abuse or dependence (excluding nicotine or caffeine) as defined in the DSM-TV-TR that has not been in sustained full remission for at least 6 months (for abuse) and 12 months (for dependence) prior to Screening.
- Positive urine drug screen prior to Baseline.
- Presence or history of a clinically significant neurological disorder (including epilepsy) or severe head injury, or any condition that has caused an abnormal EEG or that may interfere with an EEG recording in the opinion of the investigator.
- Neurodegenerative disorder (Alzheimer Disease, Parkinson Disease, multiple sclerosis, Huntington Disease, etc).
- Any unstable medical condition as determined by the principal investigator (PI).
- Any DSM-IV Axis II disorder that might compromise the study as determined by the PI.
- The subject has any other disorder for which the treatment takes priority over treatment of MDD or is likely to interfere with study treatment or impair treatment compliance.

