### **COGNITION AND FUNCTIONALITY:**

#### ***Digit Symbol Substitution Test (DSST)***

The DSST is a cognitive test designed to assess psychomotor speed of performance requiring visual perception, spatial decision-making and motor skills. The DSST consists of 133 digits and requires the subject to substitute each digit with a simple symbol in a 90-second period. The number of correct symbols within the allowed time (eg, 90 sec) is measured. It takes approximately 5 minutes to complete and score the DSST.

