## **STATISTICAL ANALYSES**

### **Primary Efficacy Analysis**

The primary endpoint is the change from Baseline in the MADRS and DSST score. The primary endpoint will be analyzed using analysis of covariance (ANCOVA), with treatment and center as fixed factors, and baseline score as covariate. The p-values, least squares (LS) treatment means, difference between the LS treatment means, and 95% CIs for the treatment differences will be displayed.

This is a pilot study that is intended to evaluate the extent of to which BNA technology can provide clinically valuable information, and to provide data that will help design a future confirmatory study. Because this is an exploratory study, no formal sample size calculation was performed; rather, sample size has been based on that which is generally accepted by the medical community for a study of this nature. In order to strengthen the level of confidence of the results, the BNA test is performed twice before the subject is given medication to provide repeatability and two additional times during the course of treatment to allow the identification of any potential trend that may occur as a result of treatment.

The relationship between changes in BNA and BNA total mean change from baseline and endpoint will be analyzed. Changes in BNA from baseline will also be analyzed by groups defined on endpoint status (e.g. response to MADRS, remission, change in DSST).

Statistical analysis should also consider the fact that changes in brain networks may be independent of symptoms or neurocognitive scores; thus, the analysis of BNA changes across treatment duration should be also performed independently. In other words, it is possible that BNA conveys information that is not found in other methods; trying to find correlations may limit the correct interpretation. Therefore, robust trends found in BNA scores should be further researched, regardless of finding correlations to symptoms or neurocognitive tests. For example, it could be that a change in BNA, without a significant change in symptoms, means that if the treatment will be continued for a few more weeks, a delayed improvement will be found; etc.

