### **Secondary Efficacy Analyses**

Change from Baseline in TMT A, TMT B, , PDQ, MGH-CPFQ, UPSA, percentage of productivity loss (WLQ), MADRS, CGI-S, and CGI-I will be analyzed at all time points (where rated) using ANCOVA model similar to the one described above for the primary endpoints.

MADRS responders (defined as a >50% decrease from Baseline), MADRS remission (defined as a MADRS total score <10). CGI-S remission (CGT-S2), and CGI-I response (CGI-I2) will be analyzed at all time points by logistic regression, adjusting for baseline score and treatment.

Proportion of cognitive dysfunction improvement that is not due to an improvement in depressive symptoms will be analyzed using a path analysis with change from Baseline in DSST score and change from Baseline in MADRS total score as endogenous variables.

C-SSRS will be summarized at all time points using descriptive techniques.

All statistical tests will be 2-sided and at the 5% level of significance. Ninety-five percent confidence limits will be presented together with the p-values.

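### Secondary outcome 5d: the unjustified 70% DSST improvement cutoff is likely to leave too few improvers among 40 subjects for a useful prediction analysis

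*Combined protocol and SAP*

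**What the plan says.** The cutoff appears once, under Secondary Outcomes, item 5d: "Prediction of cognitive improvement measured by DSST score; cutoff 70% improvement from baseline". It belongs to the item that looks at BNA before treatment. Item 5b in the same list relates pre-treatment BNA to baseline severity, including the baseline DSST.

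Other places that bear on it:

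- Main Criteria for Exclusion rules out a score of 70 or more "on the DSST at the Baseline Visit". No lower limit is given.
- The description of the test sets the ceiling: "The DSST consists of 133 digits and requires the subject to substitute each digit with a simple symbol in a 90-second period".
- Item 4 of Secondary Outcomes forms subgroups partly on cognition, for example subjects who miss the antidepressant criteria "but show improvement in cognition (based on DSST"), and gives no cutoff. The Outcome Definitions section has no DSST criterion either.
- The Primary Outcome uses the change in the number of correct DSST symbols, without dichotomising.
- Number of Subjects gives "40 subjects enrolled", and Primary Efficacy Analysis states that "no formal sample size calculation was performed".
- Appendix I schedules the DSST at screening and at Visit 10 only.

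**The concern.** A 70% rise in DSST means an endpoint of at least 1.7 times the starting score. For most scores that eligibility allows, this is a large gain over eight weeks, and the protocol neither justifies it nor says how many subjects are expected to reach it. If only a handful do, a prediction analysis with that outcome has almost no information.

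A proportional rule also asks for very different gains from different subjects: 14 symbols from a start of 20, but 35 from a start of 50. The improver class would then be made up mainly of people who started low. Any BNA feature that tracks baseline DSST would seem to predict improvement, although item 5b already examines that association.

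The pilot is meant to inform the design of a confirmatory study. An empty or misread result in 5d would weaken that use.

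**Working it through.** **No plan figure to reproduce.** The documents state no expected improver rate, DSST mean, SD or gain, and the 40 subjects do not come from a calculation.

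**Step 1: the threshold (no assumption needed).** Required endpoint = 1.7 × baseline, rounded up.

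| Baseline | Required endpoint | Gain |
|---|---|---|
| 20 | 34 | 14 |
| 30 | 51 | 21 |
| 40 | 68 | 28 |
| 41 | 70 | 29 |
| 50 | 85 | 35 |
| 60 | 102 | 42 |
| 69 | 118 | 49 |

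From 41 upwards (1.7 × 41 = 69.7) the required endpoint is at or above the score that excludes a subject at entry. The target can be reached arithmetically, since 133 / 1.7 = 78.2 exceeds every eligible baseline.

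**Step 2: expected improvers among 40 (assumed inputs).** Baseline is normal with SD 12, rounded and kept from 10 to 69; gain is normal and independent of baseline, with mean 4 to 10 and SD 7 to 10; all 40 subjects are evaluable. Expected count = 40 × P(endpoint ≥ 1.7 × baseline), by simulation. The low end is gain 4 with SD 7; the high end is gain 10 with SD 10.

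| Assumed baseline mean | Expected improvers of 40 |
|---|---|
| 55 | 0.0 to 0.7 |
| 50 | 0.1 to 1.2 |
| 45 | 0.2 to 2.0 |
| 40 | 0.5 to 3.3 |
| 35 | 0.9 to 5.0 |
| 30 | 1.6 to 7.1 |

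At mean 45, gain 10 and gain SD 8, p = 0.032 and the expected count is 1.3. The chance of no improver is (1 − 0.032)^40 ≈ 0.28, and the chance of five or more is 0.008.

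**Step 3: what would give 10 improvers.** With gain SD 8, the mean gain has to be about 14 to 15 symbols at baseline mean 30, 20 at mean 40, 24 at mean 45 and 27 at mean 50.

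**Step 4: precision.** The protocol names no method for 5d, so I use an AUC of 0.75 as a yardstick, with the Hanley–McNeil standard error for k improvers and m = 40 − k others:

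SE² = [A(1 − A) + (k − 1)(u − A²) + (m − 1)(v − A²)] / (k m), where u = A/(2 − A) = 0.600 and v = 2A²/(1 + A) = 0.643.

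For k = 3: [0.1875 + 2 × 0.0375 + 36 × 0.0804] / 111 = 0.0284, so SE = 0.169 and the 95% half-width is 1.96 × 0.169 = 0.33. The half-width is 0.57 for k = 1, 0.40 for k = 2, 0.26 for k = 5 and 0.19 for k = 10. With five improvers or fewer, the interval around 0.75 still includes 0.5.

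**Step 5: who the improvers are.** At mean 45, gain 10 and gain SD 8, improvers have a mean baseline of about 26, against about 44 for all subjects.

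**The case against.** The strongest reply is that the counts rest on inputs the documents do not supply. Eligibility sets no lower DSST limit and requires reported cognitive difficulty, so a low baseline mean is possible. A mean of 30 with a gain of 15 gives about 10 to 12 improvers. Gain may also be larger in low scorers. With an assumed baseline–gain correlation of −0.3 to −0.5 and a mean gain of 10, the counts rise to about 3 to 5 (mean 40), 4 to 7 (mean 35) and 6 to 8.5 (mean 30). This stands as a limit on certainty, although most of these counts remain small. The counts also assume no dropout, and losses would lower them.

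A second reply is that little depends on 5d. It is one sub-item of a study declared exploratory, and the primary outcome keeps DSST change on its own scale. This also stands, and it limits the reach of the point.

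A reader might infer more than the documents support:

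- **That the analysis cannot be done, or that almost nobody can qualify.** The target is below the test maximum for every eligible baseline, and the count depends on assumed inputs.
- **That BNA would look uninformative about cognition in general.** The primary outcome and the planned grouping by DSST change do not use the cutoff.
- **That items 4 and 5d hold conflicting definitions.** Item 4 gives no DSST rule at all, so a definition is missing; the 70% could even be meant for both items.
- **That a score of 70 marks a subject as too little impaired.** This is a plausible reason for the exclusion, but the protocol gives none.

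**Conclusion.** The point holds as a likely loss of information in one secondary item. The threshold arithmetic is certain: with entry limited to scores below 70, every subject starting at 41 or above must reach at least 70. The shortage of improvers is conditional on baseline SD 12, mean gain 4 to 10, gain SD 7 to 10 and independence. On those terms, 40 subjects yield about 0 to 2 improvers for baseline means of 45 to 55, and up to about 7 at a mean of 30. Ten or more needs a combination such as a mean of 30 with a gain near 15. Where improvers are few, they are mainly low scorers at baseline, so 5d would largely repeat 5b.

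The change is worth making before analysis. The continuous DSST primary outcome is not affected.

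**What to change.** In item 5d, remove the 70% cutoff. Relate pre-treatment BNA to the change in number of correct DSST symbols as a continuous outcome, with the pre-treatment DSST score as covariate. This agrees with the Primary Outcome and with the baseline-adjusted model in Primary Efficacy Analysis.

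State which score is the baseline. Appendix I has no DSST at the Baseline Visit, while Main Criteria for Exclusion refers to a score at that visit. Either name the screening score as baseline or reconcile the two sections.

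If a binary class is kept, pre-specify and justify one rule and use it in both items 4 and 5d. The choice matters. At assumed baseline mean 45, SD 12 and gain SD 8, a mean gain of 5 or 10 gives 13.0 or 22.3 expected improvers at a 20% cutoff, 6.8 or 14.1 at 30%, and 0.4 or 1.3 at 70%. These figures illustrate sensitivity and do not recommend a cutoff. If a DSST score of 70 was meant instead of a 70% rise, the text should say so.

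The cost is a sentence or two of protocol or SAP wording and no new data. The downside is that 5d would no longer give a simple improver label.

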### **BNA Analysis**

All BNA recordings will be transmitted to EIMindA for analysis.

We will use a receiver operating characteristic (ROC) curve to assess the ability of each EEG BNA group pattern to discriminate MDD cases from controls using individual BNA similarity indices. The ROC analysis uses each value across the entire range of the EEG BNA pattern as the cut-off for defining a case and compares this classification to the “true” diagnosis, as defined by the structured diagnostic interview. The ROC curve plots the sensitivity versus the false positive rate (1-specificity) across the entire range of cut-offs. This analysis generates a statistic called the area under the curve (AUC), which is proportional to the overall ability of the scale across its range of cut-offs to correctly identify both cases and non-cases.

Secondly, we will analyze the results of EEG measurement during the test within patients to identify possible predictors of treatment response. Those analyses are exploratory in nature, and they could potentially lead to develop an EEG biomarker to predict antidepressant response.

In the first stage EEG signals are pre-processed using standard methods of blind source separation followed by band pass filtering into overlapping physiological frequency bands, epoched and averaged to result with ERPs. For each band, the data is reduced into a set of discrete points that denote local extrema, the latencies and (z-score normalized) amplitudes of which are inputted to the algorithm. These activity peaks naturally contain the major conventional ERP components, but all other associated and induced peaks as well, which fully represent the significant information in the measured data. For each experimental state (i.e. pre- and post-treatment, monotherapy vs. adjunctive therapy, healthy control vs. MDD), the algorithm then searches for peaks that have latencies synchronous across subjects. Next, peak-pair patterns are identified, whether within a single electrode or between any two, such that the inter-peak intervals were also synchronous across subjects. More complicated patterns of 3 or more peaks are sought in a similar manner, until a state-unique multi-sited spatio-temporal pattern or several distinct patterns emerge – the BNA group network.

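### Item 5d tests pre-treatment BNA against a 70%-of-baseline DSST cutoff that depends on baseline DSST and, under plausible DSST values, leaves almost no improvers

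*Combined protocol and SAP*

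**What the plan says.** Item 5 of the Secondary Outcomes is introduced as "To explore changes in BNA patterns in MDD with cognitive dysfunction prior to receiving treatment with vortioxetine and" a list of four targets. The wording is loose, but 5a to 5d make sense only with pre-treatment BNA as the predictor. Item 5b is "Severity of cognition dysfunction and functionality as measured by baseline DSST, TMT-A/B, TMT-B, Stroop, MGH-CPFQ total score, UPSA, WLQ". Item 5d is "Prediction of cognitive improvement measured by DSST score; cutoff 70% improvement from baseline".

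The BNA Analysis section says "we will analyze the results of EEG measurement during the test within patients to identify possible predictors of treatment response". It calls this exploratory and names neither a model nor a covariate.

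Adjustment for baseline score appears elsewhere, but never with BNA as predictor:
- the ANCOVA for MADRS and DSST change (Primary Efficacy Analysis);
- the similar ANCOVA for other scales (Secondary Efficacy Analyses);
- the logistic regression for MADRS and CGI outcomes (same section), which does not cover the 70% DSST cutoff.

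The plan has "40 subjects enrolled", states that "no formal sample size calculation was performed", and sets the rule "All statistical tests will be 2-sided and at the 5% level of significance". The Schedule of Events (Appendix I) lists the DSST at screening and Visit 10 only.

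**The concern.** Baseline DSST sits on both sides of the analysis. It is a target of the predictor in 5b and part of the outcome formula in 5d. Because the gain required rises in proportion to baseline, low scorers clear the cutoff more easily. Some low scorers are also low through measurement error and will drift upward on retest. A BNA score that merely restates baseline DSST can then separate improvers from non-improvers.

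The pilot is meant to show whether BNA is clinically informative and to help design a confirmatory study, and the BNA Analysis section mentions a possible EEG biomarker of response. A score that adds nothing to a test taking about 5 minutes could be carried forward. Conversely, if hardly anyone meets the cutoff, 5d says almost nothing either way.

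**Working it through.** The plan gives no power, event or DSST figure to reproduce.

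**1. The cutoff.** (V10 − B)/B ≥ 0.70 is the same as V10 ≥ 1.70 × B, a gain of at least 0.70 × B.
- B = 20: V10 ≥ 34, gain 14
- B = 40: V10 ≥ 68, gain 28
- B = 69 (highest whole score below the exclusion limit of 70): V10 ≥ 117.3, gain 48.3

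The test maximum of 133 is not the constraint, since 133/1.70 = 78.2 exceeds any eligible baseline.

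**2. Assumptions (not in the documents).** N = 40, two-sided 5%, true gain unrelated to BNA.
- Set A: mean 48, SD 11, scores of 70 or more excluded, reliability 0.7 to 0.9, uniform gain 0 or 6, BNA-DSST correlation 0.4 or 0.6.
- Set B: mean/SD 45/12 or 42/10, reliability 0.8 or 0.9, mean gain 5 or 10, SD of true gain 6, correlation 0, 0.3, 0.5 or 0.7.

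**3. How many improvers.** Take mean 45, SD 12, reliability 0.8 and gain 10. Error variance per test is 144 × 0.2 = 28.8. The SD of change is √(36 + 2 × 28.8) = 9.67. A subject at the mean needs 0.7 × 45 = 31.5 symbols, which is (31.5 − 10)/9.67 = 2.2 SD above the mean gain.
- Set B: 1.2% to 6.8% improvers, or 0.5 to 2.7 of 40. The chance of none is (1 − 0.0675)^40 = 0.06 at best and (1 − 0.0123)^40 = 0.61 at worst.
- Set A: 0.01 to 0.85 of 40, with none in 41% to 99% of simulated trials.

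**4. BNA built from the observed baseline score plus noise (Set B).** The last three columns are false-positive rates.

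| Correlation | AUC, 70% status | 70% status | Percent change | Absolute change |
|---|---|---|---|---|
| 0 | 0.50 | 0.3–3.4% | about 5% | 4–6% |
| 0.3 | 0.63–0.67 | 1–9% | 9–16% | 5–7% |
| 0.5 | 0.71–0.76 | 2–19% | 16–34% | 7–11% |
| 0.7 | 0.79–0.85 | 4–34% | 29–59% | 8–18% |

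In Set A, percent change gives 15% to 41% with a gain of 6 and 7% to 25% with no gain. The 70% status gives 0% to 6.7%.

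**5. BNA built from true ability instead (Set A).** Percent change gives 5% to 7% with no gain and 7% to 17% with a gain of 6. Absolute change is then gain plus the difference of two test errors. None of these depends on true ability, so apart from the truncation at 70 its rate stays near 5%.

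**6. Visit 10 DSST on BNA plus baseline DSST.**
- BNA tracks the observed score: 4.6% to 5.3% (Set A) and 4.4% to 5.8% (Set B).
- BNA tracks true ability: roughly 8% to 34% (Set A). In Set B, 5% to 7% at correlation 0.3 and up to 26% at 0.7 with reliability 0.8. The excess arises because a single error-prone baseline score does not fully remove the influence of true ability.

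**The case against.** A reader might infer that any BNA score correlated with baseline DSST is bound to appear predictive, with false-positive rates of 15% to 41%. The documents do not support this. Those rates belong to continuous percent change, whereas 5d specifies a binary cutoff, and under the same assumptions the binary test rejects in 0% to 6.7% of trials. They also require BNA to follow the random error in a paper test. If BNA follows true ability and there is no gain, percent change rejects at 5% to 7% although BNA and baseline DSST are correlated.

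A reader might also infer that baseline adjustment cures the problem. Step 6 shows that it does so only if BNA tracks the observed score. Otherwise the adjusted model can reject more often than percent change does.

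Nor does the argument reach item 5c. MADRS and HDRS-17 remission are endpoint thresholds, and CGI-I is a clinician's rating, so none is computed from a baseline score.

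Finally, this is one secondary item in a pilot, its predictor analyses are labelled exploratory, and no unadjusted test is prescribed. All of that stands and limits the weight of the point. It does not change the dependence of the cutoff on baseline, the scarcity of improvers, or the lack of any planned analysis asking what BNA adds to baseline DSST.

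**Conclusion.** The point holds as a weakness in how 5d is defined. Improver status depends on baseline DSST by construction, and no planned model accounts for this when BNA is the predictor. A BNA score that only tracks baseline DSST can show an AUC well away from 0.5. With about 0 to 3 improvers among 40, however, the binary comparison will usually miss significance, so its main failing is that it is nearly uninformative. Inflated false-positive rates are chiefly a risk if percent change is analysed as a continuous variable: about 5% to 59% over the assumptions examined with some BNA-DSST correlation.

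The algebra of the cutoff needs no assumption. The improver counts, AUCs and error rates all rest on assumed DSST means, SDs, reliability, gains and BNA correlations. A larger gain or a lower baseline distribution would produce more improvers.

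**What to change.** In item 5d and the BNA Analysis section, specify a linear model of Visit 10 DSST (continuous) on pre-treatment BNA, with baseline DSST and centre as covariates. Report what BNA adds over baseline DSST alone. Keep the 70% cutoff as a descriptive count. State which DSST measurement is the baseline: the schedule has only the screening test, while the exclusion criterion refers to a score at the Baseline Visit.

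Interpret a non-zero BNA term as added prognostic value given the measured baseline, not as proof that BNA predicts true gain, because error in the single pre-treatment DSST leaves residual confounding. Show unadjusted absolute change in DSST, the definition used in the Primary Outcome, as a sensitivity analysis. The two analyses are close to nominal under opposite conditions (BNA tracking the observed score or true ability), so agreement between them is more persuasive than either alone.

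The cost is two degrees of freedom at N = 40 (one for baseline DSST, one for two centres), one sensitivity analysis and a few lines of text. No new data or visits are needed, and item 5c needs no change on this account.
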